4. Is found otherwise eligible for continued participation.

All consented participants who do not complete all screening assessments within the 21-day screening period or who are otherwise found to be ineligible for study participation will be

RESTRICTED

considered screen fails. With Sponsor approval, screen fails may be allowed one additional chance to return at a later date (at least 30 days past initial screen fail date). Demographic data and the reasons for not meeting eligibility criteria will be documented for all screen fails.

After the participant is deemed fully eligible and this is recorded in the Advantage eClinical system, the participant will then complete all assessments required on the day of randomization as detailed in Table 11.1 for Week 1.

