10.3 Randomization

Following the collection of the assessments required for screening and eligibility, eligible participants will be randomly assigned to BUP-Inj or PBO-Inj in a 1:1 ratio. The randomization procedure will be conducted electronically by the Advantage eClinical system. The unblinded DSC Statistician will review the randomization data on a regular basis to ensure that the scheme is being implemented according to plan. If a participant drops out of the study at any point after randomization, the randomization slot will not be re-allocated to a new participant due to the intent-to-treat nature of the study. All screening assessments must be completed before the participant is randomized and all assessments required on the day of randomization must be completed before the participant is administered any study medication.

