Cognitive Behavioral Therapy Documentation			X	X	X	X	X	X	X	X	X	X	X	X	X	X
Iowa Gambling Task and Documentation		X*														
Treatment Effectiveness Assessment																X ²
Cannabis Use Assessment			X													
Tobacco Use History (PhenX Tier 1)			X													X ²
Quality of Life (PhenX Tier 1)			X													X ²
Semi-Structured Qualitative Interview			X ^E													
Adherence Measures																
Buprenorphine-XR/Placebo Injection				X ²				X				X				
BUP-SL Dispensing				X ¹												
Laboratory Evaluations																
Urine Screening for Disease			X*												X	
Complete Blood Count			X*												X	
Blood Chemistry			X*													
Liver Function Tests			X*												X	
Disease Serology			X*												X	
Blood Sample for UTSW Repository			X*												X	
Blood Sample for NIDA Genetic Testing and Family Origin								X ^C								

Study Phase	Prescreening	Screening	Medication Phase												Follow-up
			1	2	3	4	5	6	7	8	9	10	11	12	
Study Week		-21 to -1	1	2	3	4	5	6	7	8	9	10	11	12	16
Buprenorphine Blood Levels							X ^A				X ^A			X	
Administrative and Other Forms															
Locator Form		X*			X		X			X			X		
Eligibility - Randomization (Enrollment Form)			X												
Visit Documentation Form		X+	2X	2X	2X	2X	2X	2X	2X	2X	2X	2X	2X	2X	X
Mental Health Follow-Up Assessment ^B															
End of Medication Form														X ²	
Protocol Deviation and Review ^B															
Treatment Satisfaction															X
Study Completion															X

NOTES:

X* = once during screening

X+ = at each screening visit

X^A = at each induction visit, including if additional induction visits are required during the medication phase, and on the day of first injection

X = a procedure or assessment performed once per week and preferably at the first visit of the week, unless otherwise noted

2X = a procedure or assessment performed twice per week

X¹ = on the day of induction only

X² = collected at the second visit of the week

^A Must be collected prior to administration of any medications at the visit

^B Completed as applicable

^C If consent is provided, collect sample on day of 2nd injection if possible. Otherwise, to be collected at any future visit with blood draw.

^D Collected at screening visit(s) with a UDS negative for opioids and on the day of expected randomization

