4. *Measures of mood, pain and stress*: All measures, (a) Changes in self-reported depressive symptoms as measured by the IDS-SR during Weeks 1-12, (b) Changes in self-reported anxiety symptoms as measured by the GAD-7 during Weeks 1-12, (c) Changes in self-reported mood symptoms as measured by the CAST-IRR during Weeks 1-12, (d) Changes in self-reported anhedonia as measured by the DARS during Weeks 1, 5, 9, and 12, (e) Changes in self-reported pain as measured by the P-FIBS during Weeks 1-12, and (f) Changes in self-reported stress as measured by the PSS during the Weeks 1, 5, 9, and 12 will each be analyzed using repeated-measures mixed-effects models, with terms for time, treatment group, treatment group by time interaction, baseline measure of the outcome, and any covariates. Person effects will be random and all other effects fixed.
5. *Retention*, defined as the number of visits (0-24) present and providing urine drug samples during Weeks 1-12 will be analyzed similarly as described for the secondary outcome.
6. *Measures of Infectious disease control, incidence, and risk*:
 - a. Defined as the biomarkers measured at Week 12, remaining HIV-negative for those that started the trial HIV-Negative and remaining HCV-negative for those that started the trial HCV-Negative, will be analyzed using logistic regression with HIV status and HCV status as the outcomes, respectively, and treatment group and other covariates as predictors.
 - b. Self-Reported HIV transmission risk behaviors measured at Weeks 1, 6 and 12, defined as (a) Self-reported number of new sexual partners, (b) Self-reported number of sexual partners with condomless sex who are serodiscordant or unknown serostatus, (c) Self-reported number of sexual partners with condomless sex with partners who are serodiscordant or unknown serostatus with whom illicit substance were used (chemsex), (d) For men, self-reported

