number of male sexual partners, (f) Self-reported number of episodes sharing needles, and (g) Self-reported number of episodes sharing injection equipment and paraphernalia will each be analyzed using a repeated measures mixed effects model for count data outcomes. If zero-inflation is observed a zero-inflated poisson, negative binomial, or hurdle model will be used depending on which model best fits the data. However, if an outcome has low counts, we may collapse it into a binary (presence/absence) outcome. If the data are very sparse, we may collapse across weeks and use a logistic regression model.

7. *Measures of functioning:*

- a. Changes in self-reported assessment of Quality of Life (QoL) at Week 1 and Week 12 will be analyzed using repeated-measures mixed-effects model, with terms for time, treatment group, treatment group by time interaction, baseline measure of the outcome, and any covariates. Person effects will be random and all other effects fixed.
- b. Self-reported overall functioning as measured by the Treatment Effectiveness Assessment (TEA) at Week 12 will be analyzed using analysis of covariance.
8. *Measures of adverse events:* both (a) Number and severity of adverse events reported during Weeks 1-12 and (b) Number and outcomes (non-fatal, fatal) of overdose events during Weeks 1-12 will be analyzed using Chi-square tests for each measure of AEs.
9. Self-reported measures of alcohol, tobacco and other drug use on TLFB at Weeks 1, 5, 9, and 12, and UDS results of other substance use not quantified for primary or secondary outcomes will be analyzed using a repeated-measures mixed-effects model for continuous outcome (amount of use) or binary outcome (presence/absence of use). The models will have terms for time, treatment group, treatment group by time interaction, baseline measure of the outcome, and any covariates. Person effects will be random and all other effects fixed.
10. Urinalysis results indicating a new chlamydia or gonorrhea diagnosis at Week 12 will be analyzed using a logistic regression with the presence of a Week 12 diagnosis as the outcome and treatment group and other covariates and predictors.
11. IGT at screening as a predictor of treatment response will be analyzed using the primary outcome analysis being repeated with the addition of terms for baseline IGT performance and IGT by time interaction.

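### Exploratory mixed models (16.6 items 2b, 4 and 7a): read literally, the pre-dose Week 1 value is both the baseline covariate and an outcome time point, which invalidates the QoL inference and dilutes the averaged arm effect on the other scales

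*Combined protocol and SAP*

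**What the plan says.** Section 16.6 item 7a: "Changes in self-reported assessment of Quality of Life (QoL) at Week 1 and Week 12 will be analyzed using repeated-measures mixed-effects model". The fixed part of that model is then listed: "with terms for time, treatment group, treatment group by time interaction, baseline measure of the outcome, and any covariates". The random part is given by "Person effects will be random and all other effects fixed".

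Item 4 uses the same terms for scales whose outcome times also begin in Week 1, for example "Changes in self-reported depressive symptoms as measured by the IDS-SR during Weeks 1-12" and "Changes in self-reported anhedonia as measured by the DARS during Weeks 1, 5, 9, and 12". Item 2 uses them for SOWS (2b), whose outcome times begin on the day of randomization.

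Three places fix when the Week 1 value is taken:

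- Table 11.1 gives QoL, IDS-SR, GAD-7, CAST-IRR, DARS, PSS, P-FIBS and SOWS none of the screening marks (X*, X+ or the footnote D mark). Their first collection is in Week 1.
- Section 10.2.3: once eligible, "the participant will then complete all assessments required on the day of randomization as detailed in Table 11.1 for Week 1".
- Section 10.3: "all assessments required on the day of randomization must be completed before the participant is administered any study medication".

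No section defines baseline for these models or says which term is the test of treatment. Section 16.0 promises a separate formal SAP.

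**The concern.** The only pre-treatment value of these scales is the Week 1 value. The plan lists Week 1 among the outcome times and also asks for a baseline covariate, so one number sits on both sides of the equation. At that time point the outcome equals the covariate and the expected arm difference is zero.

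Two things are at stake. An arm effect averaged over all time points includes a structural zero and understates the effect after dosing. And the Week 1 residuals do not behave like those at later visits, so a model with one residual variance and a random intercept can report the wrong standard error. QoL, with two time points, is the extreme case.

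**Working it through.** The documents give no power, standard error or effect size for these models, so there is no stated figure to reproduce.

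**Inputs.** From the plan: N = 246 at 1:1, so 123 per arm (16.1.3, 16.2); T = 2 time points for QoL, 4 for DARS and PSS, 12 for the weekly scales (16.6). Assumed: unit variance at each visit; within-person correlation r = 0.3, 0.5 or 0.7; two-sided 5% (16.4 states a level only for the primary outcome); complete data; a constant post-dose effect of 0.3 SD where an effect is needed.

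**Dilution.** The average over T time points contains one zero, so the arm effect is multiplied by (T-1)/T:

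- QoL: 1/2, so 0.30 becomes 0.15.
- DARS, PSS: 3/4, so 0.30 becomes 0.225.
- Weekly scales: 11/12, so 0.30 becomes 0.275.

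**QoL: why the model degenerates.** Let b be the Week 1 value. The slope on b is 1 for the Week 1 outcome and r for the Week 12 outcome, so the pooled slope is (1+r)/2. Write a = ((1-r)/2)². Then:

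- Week 1 residual: b(1-r)/2, with variance a.
- Week 12 residual: -b(1-r)/2 + e, with variance a + (1-r²).
- Covariance of the two: -a, which is negative. A random intercept cannot produce a negative covariance, so its variance goes to zero.

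The model then uses one pooled residual variance, s² = a + (1-r²)/2, at both visits. With k = 2/123:

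- Week 12 contrast: model variance k·s²; true variance k·[a + (1-r²)].
- Interaction: model variance 2k·s². The term in b cancels in the difference, leaving the change score, with true variance k·2(1-r).
- Type I error: 2[1 - Φ(1.96 × model SE / true SE)].

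At r = 0.5: a = 0.0625 and s² = 0.0625 + 0.375 = 0.4375. The Week 12 model SE is √(0.4375 × 2/123) = 0.084 and the true SE is √(0.8125 × 2/123) = 0.115. The ratio is 0.734 and type I error is 15.0%. The interaction has model SE 0.119 against a true 0.128, giving 6.7%.

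| r | Week 12 type I: formula / simulated | Interaction type I: formula / simulated | True variance, change score vs ANCOVA: 2(1-r)/(1-r²) = 2/(1+r) |
|---|---|---|---|
| 0.3 | 14.3% / 14.6% | 7.5% / 7.8% | 1.54 |
| 0.5 | 15.0% / 15.3% | 6.7% / 7.0% | 1.33 |
| 0.7 | 15.7% / 16.3% | 5.9% / 6.3% | 1.18 |

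The simulated columns come from 4,000 trials per setting with N = 246; the random-intercept variance was zero in essentially all of them. The QoL main-effect test errs the other way: type I error 3.0%, 3.7% and 4.3%, and power for 0.3 SD of 59%, 72% and 89%, against 68%, 77% and 91% for Week 12 ANCOVA.

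**Item 4: averaged main effect.** In balanced data the test compares person means adjusted for b. The person mean is b/T + [(T-1)/T] × (post-dose mean). The term b/T is absorbed by the covariate, so estimate and SE are both multiplied by (T-1)/T and z does not change. Simulated power at r = 0.5 agrees: 94.5% under both models for T = 4, and 98.9% under both for T = 12.

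**Item 4: last-visit contrast.** Simulated type I error is 8.1-9.0% for T = 4 and 6.1-6.7% for T = 12, against 5.5-5.9% when Week 1 is a covariate only.

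**SOWS.** Item 2b also counts any induction visits and the assessment before the first injection. Induction is the same in both arms (10.4.1), so more than one listed time point may carry no expected arm difference.

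**The case against.** The strongest reply is that the double use is inferred. Baseline is undefined, item 7a can be read as the change from Week 1 to Week 12, Section 16 calls itself general, and a formal SAP is to follow. The Table 11.1 legend also makes Week 1 timing a preference: "a procedure or assessment performed once per week and preferably at the first visit of the week, unless otherwise noted". This stands as a limit on certainty, but it does not remove the problem. The schedule offers no other source for the baseline term, and a site that collected Week 1 at the second visit would have no pre-dose value at all. Modelling change from baseline does not help either: the Week 1 change is zero for everyone, and the model is the same one reparameterised.

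Second, 16.6 never names the averaged main effect as the test. The wording about a main or interaction effect belongs to secondary outcome 1a in 16.3.2. This stands: only the averaged effect is diluted; the interaction and the Week 12 contrast are not. For QoL, however, none of the three is sound as modelled.

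A reader might infer that the overlap costs precision in all these mixed models. It does not: in item 4 the averaged test keeps its power. A reader might also take 2/(1+r) to mean that a QoL comparison with 90% power by ANCOVA falls to 74%, 80% or 85%. Those figures need a correctly calibrated change-score test. With its too-small SE the literal interaction test would reject about 80%, 84% and 87% of the time, but with inflated type I error. The defect is miscalibration more than lost power.

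Finally, the outcomes are exploratory, with no alpha or power attached. That stands and limits the weight of the point.

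**Conclusion.** The point holds in a limited form. On the natural literal reading, the QoL model is degenerate: the averaged arm effect is halved, the Week 12 contrast has type I error of about 14-17% and the interaction about 7% at nominal 5%, and the interaction's true variance is 1.18 to 1.54 times that of ANCOVA. In item 4 the averaged effect is reported at 3/4 or 11/12 of its value with unchanged power, and last-visit contrasts run at about 6-9%. SOWS shares the structure. VAS, ACSA and COWS have screening values and need not be affected.

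The figures rest on N = 246, complete data, equal variances, assumed r of 0.3 to 0.7 and a two-sided 5% level. The documents do not support a general claim of lost power across these models, nor any effect on the primary or secondary analyses.

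**What to change.** In the SAP, and in 16.6 items 2b, 4 and 7a:

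1. Define baseline as the Week 1 value taken on Day 0 before any study medication.
2. Use it only as a covariate, and start the outcome vector at the first assessment after the first injection.
3. Analyse QoL by ANCOVA at Week 12 adjusted for Week 1. Item 7b already uses ANCOVA for TEA.
4. Name the contrast to be tested for each scale.

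An equally acceptable alternative to steps 2 and 3 is to keep Week 1 as an outcome, constrain the arms to a common baseline mean, and drop the baseline covariate.

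The cost is wording; data collection and sample size do not change. The one small downside is that complete-case ANCOVA drops participants missing either QoL value. The common-baseline-mean model keeps those with only one.

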Following these considerations, we elected to avoid possible underdosing and save cost by not testing both doses of medication. We therefore chose to maximize the probability to detect a signal in this trial by using three 300mg injections, matching a study design utilized by the manufacturer in the initial OUD efficacy trials and supported by our interpretation of the existing data that the higher 300mg injections would not cause undue risk to our opioid experienced participant population. The 12-week timeframe is in accordance with the pharmacokinetic data indicating increased circulating drug approaching steady state, as well as persistence of the medication in the body for 4-6 weeks. Following an induction onto BUP using sublingual BUP film, participants will then receive 3 study injections over the course of the 12-week medication phase. Participants will be randomized 1:1 to either this active product or placebo condition to test the

efficacy of this medication to stop or reduce MA use in this population. Opioid use will be monitored and evaluated as secondary outcomes for this study.

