4.3 Risk/Benefit Assessment

The use of BUP-Inj, as Sublocade™ in this trial, has not yet been directly evaluated as mono-pharmacotherapy in those with MUD. Overall, the risks of using Sublocade™ for MUD are low. Further reducing risks, participants in this study will not be opioid naïve, will likely combine opioid use with methamphetamine use and meet criteria for mild OUD or demonstrate opioid misuse, which increases acceptability of this putative mono-pharmacotherapy strategy. The study will be conducted under an IND (Investigational New Drug) application, which strengthens oversight and monitoring of the study, with emphasis on evaluating safety and early efficacy. Other than the primary substance used by this population, no other existing differences are believed to increase the risks of using this medication as all other safety guidelines for use of BUP-Inj will be followed as detailed in the package insert for Sublocade™.

There is a risk to untreated MUD, especially in the setting of opioid co-use, particularly ongoing risks for opioid overdose⁶. For participants assigned to the BUP-Inj condition, risks for opioid overdose will be reduced due to the partial agonist properties of BUP. Naloxone overdose reversal kits will be provided to participants in both conditions with instructions to participants and their friends/family members on their use in the setting of overdose in order to address opioid overdose risks. There remain risks for MA overdose for participants in both conditions; however, the risks for opioid overdose are reduced substantially for participants assigned to BUP-Inj and for participants in both conditions who are given naloxone reversal kits. Regular monitoring of ongoing opioid use during the trial allows for identification of those who warrant discontinuation of trial participation and immediate referral to treatment for their opioid use.

Ongoing risks for opioid overdose, adverse events related to BUP-Inj and for events related to ongoing MA use will be assessed at a safety follow-up visit during Week 16 of the study.

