 - a. Changes in self-reported assessment of Quality of Life (QoL) at Week 1 and 12
 - b. Self-reported overall functioning as measured by the Treatment Effectiveness Assessment (TEA) at Week 12

RESTRICTED

8. Measures of adverse events:
 - a. Number and severity of adverse events reported during Weeks 1-12
 - b. Number and outcomes (non-fatal, fatal) of overdose events during Weeks 1-12
9. Self-reported measures of alcohol, tobacco and other drug use on TLFB at Weeks 1, 5, 9, and 12, and UDS results of other substance use not quantified for primary or secondary outcomes.
10. Urinalysis results indicating a new chlamydia or gonorrhea diagnosis at Week 12
11. IGT performance at screening

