16.9 Safety Analysis

Treatment emergent adverse events (AEs), including treatment emergent serious adverse events (SAEs), will be summarized by presenting the number of events, number of participants experiencing AEs, and the severity and relatedness of adverse events by treatment arm. All adverse events will be coded using MedDRA® (The Medical Dictionary for Regulatory Activities). The number and proportion of participants experiencing each treatment emergent AE will be provided overall and by treatment arm. Treatment emergent adverse events will be summarized by System Organ Class (SOC) and Preferred Term (PT). If a participant experiences multiple episodes of an event, then the event is only counted once. Detailed listings of treatment emergent adverse events and non-treatment emergent events in the safety population by treatment arm will be provided and include severity, relationship to study medication(s), and action taken, as available. The criteria for an immediate study review by the DSMB will be monitored closely. These criteria are either (1) three or more participants experience severe adverse reactions; (2) four or more participants have four consecutive positive urine toxicology screens for opioid use,

and have been reevaluated through any means as having moderate to severe opioid use disorder; or (3) one or more SUSAR.

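### Section 16.6 item 8 does not state the unit of analysis for its chi-square tests of adverse events and overdoses, has no rule for sparse cells, and stops the only between-arm test at Week 12

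*Combined protocol and SAP*

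**What the plan says.** Section 16.6 item 8 covers two measures. The first is "Number and severity of adverse events reported during Weeks 1-12". The second, in the same words as Section 7.3, is "Number and outcomes (non-fatal, fatal) of overdose events during Weeks 1-12". Both "will be analyzed using Chi-square tests for each measure of AEs". Item 8 gives no unit of analysis, method for repeat events, allowance for unequal follow-up, or rule for small expected counts.

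Section 16.9 is a separate safety analysis. Treatment-emergent AEs are "summarized by presenting the number of events, number of participants experiencing AEs", with severity and relatedness by arm. It adds: "The number and proportion of participants experiencing each treatment emergent AE will be provided overall and by treatment arm". On repeats it says: "If a participant experiences multiple episodes of an event, then the event is only counted once". It plans no between-arm test, does not name overdose, sets no Week 12 limit, and does not say when the treatment-emergent period ends.

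On timing, Section 10.4.2 places the last injection at the beginning of Week 9, and Section 4.2.3 refers to "persistence of the medication in the body for 4-6 weeks". Section 4.3 says that ongoing risks of opioid overdose and AEs related to the study drug "will be assessed at a safety follow-up visit during Week 16 of the study". Table 11.1 schedules AE collection at that visit.

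**The concern.** The measures are worded as numbers of events. The direct way to apply a chi-square test to them is to compare total events by arm. That test is valid only if events are independent, and one participant can report many AEs. If some people report many and others few, the arm totals vary more than the test allows, and a chance imbalance can look like a safety difference.

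Overdoses raise two other problems. They may be too few for the chi-square approximation, more so if split into fatal and non-fatal. The test window also closes about when the stated persistence of the last dose begins to run out. Sections 4.2.4 and 4.3 rely on lower opioid overdose risk in the active arm as part of the ethical and risk/benefit case. The only planned between-arm overdose test leaves out the weeks in which that difference could shrink.

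**Working it through.** Item 8 states no figure, so there is nothing to reproduce. The question is how each reading of it behaves.

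**Inputs.** 246 participants (Section 16.2) randomised 1:1 (Section 16.1.3) gives n = 123 per arm. The nominal level of 5% is assumed, because Section 16.4 sets 5% for the primary outcome only. The documents give no AE rates. Assumed: a mean of m events per person, and negative binomial dispersion k (smaller k means more variation between people; k infinite is Poisson). There is no true difference between arms.

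**Event as unit.** With arm totals a and b, the statistic is (a − b)²/(a + b) on 1 df. The variance of a − b is 2nm(1 + m/k), while the test assumes 2nm. The inflation is therefore V = 1 + m/k, and the true error rate is 2[1 − Φ(1.96/√V)]. Example: m = 2 and k = 1 give V = 3, 1.96/√3 = 1.13, and an error rate of 0.258.

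**Participant as unit.** A 2×2 chi-square on participants with at least one event.

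Both were also simulated (40,000 replicates per setting):

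| m | k | V | Formula, events | Simulated, events | Simulated, participants |
|---|---|---|---|---|---|
| 1 | Poisson | 1.00 | 0.050 | 0.050 | 0.053 |
| 1 | 2 | 1.50 | 0.110 | 0.105 | 0.045 |
| 1 | 1 | 2.00 | 0.166 | 0.167 | 0.048 |
| 2 | 2 | 2.00 | 0.166 | 0.166 | 0.052 |
| 2 | 1 | 3.00 | 0.258 | 0.257 | 0.052 |
| 3 | 2 | 2.50 | 0.215 | 0.215 | 0.055 |
| 3 | 1 | 4.00 | 0.327 | 0.327 | 0.053 |

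At m = 0.5 the simulated event-level rate is 0.080 (k = 2) or 0.107 (k = 1). For rare events such as overdose (m = 0.05 to 0.1, from Poisson to k = 0.5) it is 0.046 to 0.076. The participant-level test stays within 0.045 to 0.055 in every setting.

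**Sparse cells.** With equal arms, T affected participants give an expected count of T/2 per arm. A count of 5 needs T = 10, and 10/246 = 4.1% of the sample. With T = 4, all in one arm, the uncorrected chi-square is (4/123)² / [(4/246)(242/246)(2/123)] = 4.07, above the critical value of 3.84. The chance of such a 4-0 split in either direction is (122/245)(121/244)(120/243) = 0.12, and this is also the two-sided Fisher p-value. So at T = 4 the chi-square test rejects 12% of the time and Fisher's test never does. With T = 6 both reject only 6-0 splits, and each has conditional size 2.9%.

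**Window.** Four to six weeks from the start of Week 9 ends between the start of Week 13 and the start of Week 15. Item 8 stops at the end of Week 12, at or before that point.

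**The case against.** A reader might infer that the plan treats repeat events as independent and that its safety error rates are therefore wrong. The documents do not support that. Item 8 never names the unit, and a participant-level chi-square holds about 5%. Section 16.9 shows that participant-level counting is planned elsewhere, and Section 16.0 says a formal SAP will follow. This stands. It does not settle item 8, because the count-once rule is not stated to apply there. That rule covers repeats of the same event and would not merge different AEs in one person.

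A reader might also infer that safety data from Weeks 13-16 are discarded. They are not. AEs are collected at Week 16, ongoing AEs are followed to resolution or 30 days after the last visit (Section 11.3.10), and Section 16.9 has no Week 12 limit. What is missing is a between-arm comparison over that period. The Weeks 1-12 window is also deliberate: Section 5.3 frames these objectives around the 12-week medication phase. That is a reason to keep that comparison and add a second one.

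The assumed AE rates may be high. Side effects recorded after sublingual dosing, injection-site reactions, and withdrawal captured on the scheduled scales are not duplicated as AEs unless serious (Sections 11.3.3, 11.3.4 and 17.17.3). This lowers the likely mean. At 0.5 events per person the inflation falls to 8-11%.

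Finally, the analysis is exploratory, and Section 16.4 claims no error control for it. That limits how much is at stake, but these would still be the trial's only between-arm safety p-values.

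**Conclusion.** The defect is an unspecified test, not a test shown to be invalid. If events are the unit, the AE comparison rejects about 11-33% of the time at a nominal 5%, for assumed means of 1-3 events per person and dispersion 2 to 1. The inflation disappears if counts are Poisson and is small for rare overdoses (about 5-8%). If participants are the unit, there is no inflation. Event-level severity tables would share the independence problem. No figure is put on that, because it depends on how severity correlates within a person, which the documents do not say.

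For overdoses, the problems are sparse cells below about 10 affected participants in all, and a test window that ends by the time stated persistence runs out. The descriptive summaries in Section 16.9 do not fill that gap. Section 16.6 item 6b already allows count models, and collapse to presence or absence, for other counts. Item 8 can follow the same pattern. It is worth changing because the change is cheap and is useful whichever unit was intended.

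**What to change.** Rewrite Section 16.6 item 8, and carry it into the formal SAP, as follows:

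- State the participant as the unit. Compare the arms on any AE, worst severity grade per participant, and any overdose, by chi-square, or by Fisher's exact test when expected counts are below 5.
- If numbers of events are also compared, use negative binomial regression, or Poisson regression with robust standard errors, with a person-time offset.
- Keep the Weeks 1-12 comparison and add the same by-arm comparison through Week 16.

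It would also help for Section 16.9 to say when the treatment-emergent period ends.

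The cost is a little more exploratory analysis and a matching wording change to the window in Sections 5.3 and 7.3 and the synopsis. No new data are needed, because the Week 16 visit is already scheduled.
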